7.3 Evaluation During Study Intervention

7.3.1 Study Visit 2

Study Visit 2 will occur 3 months (\pm 1 month) after the initiation of the intervention. Participants will be told to fast for 8 hours before the study visit. Fasting instructions will be provided to participants prior to their study visit, and participants will receive a phone call reminder the day before the visit to fast overnight. The following procedures/evaluations will be performed during this visit:

1. Review medical history, medications, and laboratory test results
2. Physical exam including measurement of weight and symptom assessment
3. Vital signs assessment: blood pressure, heart rate, respiratory rate, and oral temperature
4. ECOG performance status
5. Pregnancy test for women of child-bearing potential. Women who have had a hysterectomy, both ovaries removed, or a tubal ligation will not be required to have a pregnancy test.
6. Blood collection for clinical labs (approximately 10 mL). Laboratory blood tests will be done for a Complete Blood Count and Automated Differential (CBDF), a Complete Metabolic Panel (CMPL), and a Lipid Panel to monitor for potential adverse effects of the intervention and to confirm that laboratory levels meet the eligibility requirements for continuation in the trial (See Appendix A). If lab results within 30 days prior to this visit for any of these tests are available in the medical record, the blood test(s) will not be done.
7. Blood collection for research purposes (26 mL): 6 mL will be collected for measurement of protocol-specific biomarkers (serum concentrations of cytokines, chemokines, and adhesion molecules), and 20 mL will be banked for DNA extraction and future studies.

8. Fecal specimen for measurement of fecal elastase. A stool collection kit and instructions will be provided to the participant before the scheduled visit. The specimen will be self-collected at home. The participant will receive a phone call reminder the day before the visit to collect the fecal specimen and bring it to the study visit.
9. Self-administered QLQ-C30 and QLQ-PAN28(CP) to assess quality of life and pain level
10. Review of conformance with inclusion /exclusion criteria
11. Collect study agent and diary
12. Assess compliance (pill count)
13. Review study diary
14. Assess adverse events
15. Dispense study agent and diary. Each participant will be given a 3-month supply of the study agent (1 bottle of 120 capsules).
16. Endoscopic pancreatic function test (ePFT) and simultaneous esophagogastroduodenoscopy (EGD) and fasting pancreatic fluid to measure secretin-stimulated peak bicarbonate concentration; cytokines, chemokines, and adhesion molecules.

7.3.2 Telephone Calls and Email/Text Messages

Study participants will be followed during intervention via telephone calls every four weeks (± 7 days) by the clinical research staff to assess compliance and adverse events. Participants who report having taken $< 80\%$ of the study drug doses between phone calls, or whose pill count at a study visit reveals $< 80\%$ compliance, will be called every two weeks (± 3 days) to monitor compliance. In addition, participants will receive a phone call the day before each scheduled study visit to remind them to fast overnight and to collect a fecal specimen and bring it to the study visit. Participants will also be reminded to bring any leftover study drugs and the study diary with them to the visit. Study participants will also be called during the week before their final visit (Visit 3) to remind them to take the study drug every day until the visit appointment.

Participants who opt to receive reminders for study medication intake via email or text messages will be contacted by the study staff during the first week of study and further as needed. The study staff will send emails or text messages on cellular phone; participants will be encouraged to respond to these messages indicating if the study drug has been taken. These responses will be used to assess compliance and will be reviewed at weekly phone contact. For participants who miss more than one dose in a week, the email/text reminders will continue further into dosing period. Since agent compliance is very important during the final week of the intervention, text/email messages will be sent to all study participants who opt to receive these reminders.

The following information will be collected during the telephone calls:

1. Medication compliance review. Participants will be asked if they missed any doses of medication, and the dates of all missed doses will be recorded.
2. Concomitant medication review
3. Adverse events. Participants will be asked if they have experienced any of the following symptoms to assess adverse events:
 - a. Upper respiratory infections
 - b. Headache
 - c. Abdominal pain
 - d. Constipation
 - e. Nausea / Vomiting

4. Additional symptoms experienced by participants will be recorded to assess adverse events

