Fecal specimen. A fecal specimen will be collected from participants at Study Visits 1, 2, and 3 for measurement of fecal elastase. A stool collection kit and instructions will be provided to the participant before the scheduled visit. The specimen will be self-collected at home and brought to the study visit.

Blood specimen. A blood specimen (approximately 10 mL) will be collected from patients at the Screen 2 visit for blood tests to confirm eligibility. A Complete Blood Count and Automated Differential (CBDF) [for hemoglobin, leukocytes, neutrophils, and platelets] and a Comprehensive Metabolic Panel (CMPL) [for total bilirubin, liver enzymes (AST/ALT), and creatinine] will be done to confirm that laboratory levels for acceptable organ, hepatic, and renal function are within the eligibility requirements. Alkaline phosphatase and glucose are also required at this visit to establish baseline levels but are not necessary for eligibility verification. See Appendix A for Clinical Laboratory Minimum Test Requirements. If a patient's lab results within 35 days before the Screen 2 visit are available in the medical record and are within eligibility range, their blood will not be drawn at the Screen 2 visit. Otherwise, the patient's blood will be drawn to confirm eligibility.

A blood specimen (approximately 36 mL) will be collected from each participant at Study Visits 1, 2, and 3. Approximately 10 mL of blood will be drawn for laboratory blood tests to monitor for potential adverse effects of the intervention and to confirm that laboratory levels meet the eligibility requirements for continuation in the trial. A Lipid Panel will be done at all study visits; a CBDF and a CMPL will be done at Study Visits 2 and 3; hemoglobin A1C will be measured at Study Visits 1 and 3; and creatine phosphokinase (CPK) will be measured at Study Visit 1 only. See Appendix A for Clinical Laboratory Minimum Test Requirements. Twenty-six mL of blood will be collected for research purposes. Six mL of blood will be drawn for measurement of serum concentrations of protocol-specific biomarkers (cytokines, chemokines, and adhesion molecules), and 20 mL of blood will be drawn for DNA extraction and use in future studies.

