5.6 Dose Modification

No dose modifications are planned. The study agent will be stopped in the event of an AE \geq grade 3 considered possibly, probably, or definitely related to the study agent. The study agent will be restarted after resolution. One of the common side effects of statin medication is myalgia (muscle pain with normal creatine phosphokinase (CPK) level), and rarely this is associated with statin myopathy (muscle weakness or other muscle injury with or without elevation in CPK level). In randomized controlled trials of standard dose statin therapy, the risk is very low (<1%). We will measure levels of CPK in the blood drawn at the first study visit to establish a patient-specific reference for this indicator of muscle toxicity. During the trial, if the participant reports unexplained muscle pain or weakness, CPK will be tested again to check for elevation. The study agent will be temporarily discontinued in subjects experiencing grade 1 or greater myopathy (unexplained muscle symptoms *and* creatine phosphokinase (CPK) > 2.5 times institutional ULN) or hepatotoxicity (ALT or AST > 1.5 times institutional ULN) that is considered possibly, probably, or definitely related to the study agent. Resolution of myopathy or hepatotoxicity will be evaluated with follow-up laboratory blood tests 4 weeks after the elevated levels occur. If the lab test results are still elevated after 4 weeks, the study agent will be discontinued permanently and the participant's primary care physician will be notified of the abnormal tests. If the lab test results return to normal levels, participant will go back on the study agent.

Because dose modification could lead to lack of dose homogeneity that may impair the research objectives, we will stop the intervention in patients who initiate drugs that require dose modifications of simvastatin below 40 mg: lomitapide, verapamil, diltiazem, dronedarone, amiodarone, amlodipine, or ranolazine.

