6.2 Reported Adverse Events and Potential Risks

The most common (incidence $\geq 5.0\%$ patients) reported adverse events (AEs) are upper respiratory infection, headache, abdominal pain, constipation, and nausea. Other AEs reported in clinical trials ($<5\%$) were diarrhea, rash, dyspepsia, flatulence, and asthenia.

Persistent increases in serum transaminases (to more than 3 x ULN) have occurred in approximately 1% of patients who received simvastatin in clinical studies. When drug treatment was interrupted or discontinued in these patients, the transaminase levels usually fell slowly to pretreatment levels. The increases were not associated with jaundice or other clinical signs or symptoms. It is recommended that liver function tests be performed before the initiation of treatment, and thereafter when clinically indicated.

Simvastatin occasionally causes myopathy manifested as muscle pain, tenderness or weakness with creatine kinase above 10 x ULN. Myopathy sometimes takes the form of rhabdomyolysis with or without acute renal failure secondary to myoglobinuria, and rare fatalities have occurred. Predisposing factors for myopathy include advanced age (≥ 65 years), female gender, uncontrolled hypothyroidism, and renal impairment. The risk of myopathy, including rhabdomyolysis, is dose related. The risk of myopathy and rhabdomyolysis is increased by high levels of statin activity in plasma. Simvastatin is metabolized by the cytochrome P450 isoform 3A4 (CYP3A4). Certain drugs which inhibit this metabolic pathway can raise the plasma levels of simvastatin and may increase the risk of myopathy. These include itraconazole, ketoconazole, posaconazole, voriconazole, the macrolide antibiotics erythromycin and clarithromycin, and the ketolide antibiotic telithromycin, HIV protease inhibitors, boceprevir, telaprevir, the antidepressant nefazodone, cobicistat-containing products, or grapefruit products. Combination of these drugs with simvastatin is contraindicated. If short-term treatment with strong CYP3A4 inhibitors is unavoidable, therapy with simvastatin must be suspended during the course of treatment.

Increases in HbA1c and fasting serum glucose levels have been reported with HMG-CoA reductase inhibitors, including simvastatin.

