The CMPL and CBDF test results will be utilized to screen for any issues that could be related to an adverse event or affect eligibility for the trial. CBDF and CMPL lab results from the Screen 2 eligibility visit will be used to establish patient-specific references prior to initiation of therapy. If blood tests were not done at the Screen 2 visit for a CBDF and CMPL; and lab results within 30 days prior to Study Visit 1 for these tests are not available in the medical record, a CBDF and CMPL will be done at Study Visit 1. The Lipid Panel includes tests for cholesterol, high density lipoprotein cholesterol, low density lipoprotein cholesterol, and triglycerides. Since the study agent is a cholesterol lowering agent, we feel that it is important to establish baseline lipid levels prior to initiating the study agent (Study Visit 1) and to monitor lipids at subsequent study visits. Hemoglobin A1C is used to assess glucose control in insulin-dependent diabetics whose glucose levels are very labile and in whom single blood glucose measurements may not accurately reflect the level of control present over the preceding few weeks. Glucose and hemoglobin A1C will be used to establish a baseline (Study Visit 1) for monitoring adverse events (incident diabetes) during the trial. CPK will be tested to establish a baseline for monitoring myopathy, a rare complication associated with the study agent (<1%). CPK will be measured at Study Visit 1 to establish a patient-specific reference for this indicator of muscle toxicity. If the participant reports unexplained muscle pain or weakness during the trial, CPK will be tested again to check for elevation.

Twenty-six mL of blood will be collected for research purposes. Six mL of blood will be drawn into a red top serum vacutainer tube for measurement of protocol-specific biomarkers (cytokines, chemokines, and adhesion molecules). Twenty mL of blood will be drawn into three vacutainer tubes, including one 6 mL red top serum tube and two 7 mL lavender top EDTA tubes, for DNA extraction and use in future studies. The blood will be collected and processed as specified in the Laboratory Manual. Processed specimens will be stored at -80°C.

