APPENDIX A

Clinical Laboratory Minimum Test Requirements

Clinical labs must include at least the following tests. It is acceptable to do additional tests if they are included in the blood panels at your institution.

Blood Hematology: Complete Blood Count and Differential	Blood Chemistry: Comprehensive Metabolic Panel	Lipid Panel *	Other Blood Tests
Hemoglobin Platelet count White blood cell count (WBC, leukocytes), total Neutrophil count, absolute	Alanine aminotransferase (ALT (SGPT)) Aspartate aminotransferase (AST (SGOT)) Alkaline phosphatase (ALP) Bilirubin, total Creatinine Glucose	Total cholesterol High density lipoprotein (HDL) cholesterol Low density lipoprotein (LDL) cholesterol Triglycerides	Hemoglobin A1C (HbA1C) † Creatine phosphokinase (CPK) §

* Lipid panels will be done at Study Visits 1, 2, and 3.

† Hemoglobin A1C will be measured at Study Visits 1 and 3.

§ Creatine phosphokinase (CPK) will be measured at Study Visit 1 to establish a patient-specific reference for this indicator of muscle toxicity. If the patient reports unexplained muscle pain or weakness during the trial, CPK will be tested again to check for elevation.

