APPENDIX C

Study Diary

Statin Therapy to Reduce the Risk of Recurrent Pancreatitis

Please bring your completed diary and your study drug supply, including empty bottles, with you to every study visit. This will help us keep track of your study drug and how well you are tolerating it.

Protocol Number: NWU2014-04-01 **Site:** _____
Participant Study ID: _____ **Participant Name:** _____
Date Study Drug Dispensed: _____ **Participant Signature:** _____

Instructions

Complete one line in the table for each day you take the study drug.

- Take your study drug once per day at bedtime or with an evening meal. Take the capsule at the same time every day. Please swallow the capsule whole and do not chew, crush, or open it.
- Record the date and time of day you took the study drug.
- If you notice any side effects such as headache, abdominal pain, constipation, nausea or vomiting, respiratory infection, or mild skin rash, or if you have any comments please record them in the Side Effects/Comments column and tell the study staff when they call you.
- If you miss a dose of the study drug, take it as soon as you remember. Do not take the drug if it has been more than 12 hours since you missed your last dose. Wait and take the next dose at your regular time. Do not take 2 doses of the study drug at the same time. Please write the reason for missing a dose in the Side Effects/Comments column.
- Using this pain scale, write a number for the amount of pain you feel **today** in the Pain Level column.

0	1	2	3	4	5
No pain	Very mild pain	Mild pain	Moderate pain	Severe pain	Very severe pain

Day	Date	Time Study Drug Taken	Pain Level	Side Effects/Comments
1		____:____  a.m. /  p.m.		
2		____:____  a.m. /  p.m.		
3		____:____  a.m. /  p.m.		
4		____:____  a.m. /  p.m.		
5		____:____  a.m. /  p.m.		
6		____:____  a.m. /  p.m.		
7		____:____  a.m. /  p.m.		
8		____:____  a.m. /  p.m.		
9		____:____  a.m. /  p.m.		
10		____:____  a.m. /  p.m.		

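### The grade 1 myopathy interruption in 5.6 relies on participants reporting muscle symptoms, but neither the telephone symptom list nor the diary examples prompt for them

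*Combined protocol and SAP*

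**What the plan says.** **The rule and its trigger.** Under 5.6 the agent is temporarily discontinued for grade 1 or greater myopathy, defined as unexplained muscle symptoms together with CPK above 2.5 times the institutional ULN, if at least possibly related to the agent. The on-treatment test is conditional: "if the participant reports unexplained muscle pain or weakness, CPK will be tested again to check for elevation". Appendix A repeats the condition: "If the patient reports unexplained muscle pain or weakness during the trial, CPK will be tested again to check for elevation". The only scheduled test is at baseline. Section 3 states that "creatine phosphokinase (CPK) will be measured at Study Visit 1 only", and the 7.1 schedule agrees. Section 7.6 gives the purpose: "CPK will be tested to establish a baseline for monitoring myopathy".

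**What the protocol says about muscle symptoms.** Section 5.6: "One of the common side effects of statin medication is myalgia". Section 6.2: "Simvastatin occasionally causes myopathy manifested as muscle pain, tenderness or weakness".

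**What participants are asked.** For the calls made every four weeks, 7.3.2 item 3 says "Participants will be asked if they have experienced any of the following symptoms to assess adverse events". It then names five: headache, constipation, abdominal pain, nausea or vomiting, and upper respiratory infection. Item 4 provides for recording other symptoms. The Appendix C diary instruction reads "If you notice any side effects such as headache, abdominal pain, constipation, nausea or vomiting, respiratory infection, or mild skin rash" and goes on to ask for an entry in the comments column and for the staff to be told at the next call.

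**The concern.** The stop rule needs a symptom and a laboratory value, and the laboratory value is obtained only once the symptom is reported. Eliciting the symptom is therefore the first step of the rule. The two tools used between visits for that purpose name other symptoms and omit this one. The diary refers the participant to the call, and the call does not ask about muscle.

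At stake is the safety of an individual participant. Someone with mild muscle pain who puts it down to exercise or to their illness may not mention it. No CPK would then be drawn, dosing at 40 mg would continue, and an interruption meant to act at grade 1 would not be triggered until a later contact or a more severe event.

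**Working it through.** The plan states no figure to reproduce here. The check has two parts: setting each collection point beside the trigger in 5.6, then sizing the gap.

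**1. Where a muscle symptom could surface after Study Visit 1**

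| Collection point | Names a muscle symptom? | What it offers |
|---|---|---|
| 7.3.2 item 3, calls every four weeks | No (0 of 5 items) | Direct questions on other symptoms |
| 7.3.2 item 4 | No | Records additional symptoms; does not say how they are elicited |
| Appendix C, examples | No (0 of 6) | The call-list symptoms plus mild skin rash; examples only, not a closed list |
| Appendix C, daily record | No | 0-5 pain score without location; free-text column |
| Section 3, physician assessment, Months 3 and 6 | Not specified | Interval symptom history |
| QLQ-PAN28(CP) item 42, Visits 2 and 3 | Weakness in the limbs | Past week only; not linked to CPK testing |
| QLQ-C30 items 9 and 12, Visits 2 and 3 | No | General pain and weakness, past week |
| 5.4 | No | General symptom monitoring; immediate call for a serious reaction |

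Only one on-treatment question names anything close to the trigger. It sits in a quality-of-life form with no instruction to act on the answer. Visit 3 is the last day of study drug (7.1, footnote 6), so of the two on-treatment visits only Visit 2, at 3 months ± 1 month, can lead to an interruption. Before and after it, the calls and the diary carry most of the load.

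**2. Number of contacts affected**

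- Six months is about 26 weeks, and 26 / 4 = 6.5, so about 6 calls per participant.
- In the simvastatin arm (n = 20, section 5.1): 6 × 20 = about 120 calls using a list with no muscle item.

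**3. Expected myopathy in the simvastatin arm**

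Expected cases = 20 × p; chance of at least one = 1 − (1 − p)^20.

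- p = 0.08% (section 2.2, 40 mg): 20 × 0.0008 = 0.016 cases; chance 1.6%.
- p = 1% (the bound in 5.6, stated as under 1%): 20 × 0.01 = 0.2 cases; chance 18.2%. Both are upper limits.

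Two uncertainties pull in opposite directions. In the database behind the 0.08%, 60% of patients were in studies with median follow-up of at least 4 years, so that rate probably overstates a 6-month risk. Against this, 6.2 describes myopathy with creatine kinase above 10 times ULN, whereas 5.6 acts at 2.5 times. If the 0.08% rests on the stricter definition, events meeting the 5.6 rule could be more frequent. The documents give no rate for them.

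**4. The trigger symptom**

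The documents give no myalgia rate. As an assumption only, rates of 1%, 5% and 10% give 20p = 0.2, 1 and 2 simvastatin participants with the symptom. The upper values fit poorly with 6.2, whose lists of events at 5% or more and below 5% do not include myalgia, although 5.6 calls it common. The share of such participants who would stay silent without a prompt is unknown, so the number of missed CPK tests cannot be estimated.

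**The case against.** The strongest reply is that nothing prevents a participant from reporting muscle pain. Item 4 of the call list is open, the diary examples are illustrative, the diary takes a daily pain score and free text, and a gastroenterologist takes an interval symptom history at Months 3 and 6. The five call items also have a rationale: they are the events that 6.2 reports in at least 5% of patients. All of this stands, and it limits the point to a missing prompt. It does not explain why the one symptom on which a stop rule depends is left to the open item.

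Three stronger readings are tempting, and the documents do not support them.

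- A reader might infer that the agent can be stopped for muscle toxicity only through the CPK rule. Section 5.6 also stops it for any related adverse event of grade 3 or above, with no CPK condition. The gap concerns grade 1-2 symptoms.
- A reader might infer that CPK should be scheduled on treatment because ALT and AST are drawn at Visits 2 and 3. The comparison is weak. Hepatotoxicity in 5.6 is defined by laboratory values alone, while the myopathy rule also requires symptoms, so a raised CPK without symptoms could not meet it.
- A reader might infer that participants are never told to report muscle pain. The consent form is not among the reviewed text and may say so. That would lessen the consequence, but it would not change what 7.3.2 directs staff to ask.

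**Conclusion.** The point holds as a minor safety improvement. The grade 1 interruption in 5.6 depends on a participant's report, and the call list (0 of 5 items) and the diary examples (0 of 6) do not ask for it. The conclusion rests on the stated content of those lists and on the conditional CPK retest, both of which are explicit.

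The likely consequence is small. Expected myopathy is 0.016 cases at 0.08% and below 0.2 at under 1%, and the added benefit of a prompt cannot be quantified without a myalgia rate and a rate of non-reporting. A reader might also infer a bias in the trial's results. There is no basis for that here: both arms are asked the same questions, and neither the endpoints nor the analysis depends on this list.

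**What to change.** Add *unexplained muscle pain, tenderness or weakness* as a sixth item in 7.3.2 item 3 and to the side-effect examples in Appendix C. Add one diary line asking the participant to call the study doctor promptly if it occurs, with a blank for the site's number. A positive answer leads to the CPK retest that 5.6 already prescribes. The CPK schedule, thresholds and dosing rules stay as they are.

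The cost is a small change to two forms and routine IRB review. Asking directly will also bring up non-specific aches in both arms. If an assumed 1%, 5% or 10% of the 30 participants report them, that means 0.3, 1.5 or 3 extra CPK tests (30 × 0.01, 30 × 0.05, 30 × 0.10), at one test each.
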